### a. Procedures

1500 participants (adults, undergraduate, graduate students) recruited by research personal at a booth set up on or near the Stanford University campus. They will have the option of completing the study at the booth, or scheduling an appointment to participate at LPCH at a later time to do all the study. If interested in the study, the research staff will gauge their preferred availability to participate in the study. During the day of their scheduled study appointment, the research assistant will review the study, go over the consent forms, and answer any questions they may have about the study. Exclusion criteria includes (i) patients who do not consent (ii) are currently taking beta blockers or other chronotropic heart medication(s) (iii) have a history of severe motion sickness (iv) currently have nausea (v) currently experiencing seizures (vi) are clinically unstable (vii) have taken pain medications in the last 12 hours Inclusion criteria includes (i) greater than 18 years of age (ii) English speaking (iii) hearing intact

#### PHASE 1

Part 1a: 3 groups of 250 healthy volunteers will be recruited for this 2 part study. Once they consent to participate in the study, the research personnel will do a Sensory perception threshold (time, amplitude) captured via biosensors (Neurometer). Then the first group of 250 participants will be randomized into either control arm (they will not receive any kind of distraction, no technologies) or the use of Virtual Reality. The second group of 250 will be randomized into Active VR, they will play a game or Passive VR, they will be watching a movie in the VR headset. And the third group of 250 will be randomized into Augmented Reality (AR) or VR. The three groups will wait 5 minutes and each participant will switch to the opposite group (i.e. in the first group, VR group will switch to no VR group). Part 1b: Ice bath: Participants immerse hand in ice bath and starting again with their original assigned group (see attached Dahlquist et al., 2007) and keep hand submerged as long as they can withstand the cold or until 4 minutes

have elapsed, whichever comes first. Participants will not be told of the specifics of the time limit, to avoid competitiveness and expectations and will be asked for pain scores every 30 seconds.

## PHASE 2

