Evaluating the Effectiveness of Immersive Technologies, Virtual Reality and Augmented Reality, to Increase Pain Threshold During Ice Immersion

NCT04196686
February 23, 2022

[name], Principal Investigator
Stanford University
Stanford, California 94305

Statistical Analysis Plan

Outcomes

The primary outcome was Virtual Reality (VR)'s effect on pain tolerance. The first secondary outcome was VR's effect on perceived pain intensity. Our final secondary outcome was to investigate the effects of VR on modulating sympathetic response in the presence of painful stimuli. We made no changes to trial outcomes after the trial commenced.

Measures

We assessed pain tolerance by measuring the duration that participants kept their hand immersed within the ice bath (in seconds). Given that the cold pressor test produces an uncomfortable experience, we considered longer duration within the ice bath to represent increased pain tolerance.

Our first secondary outcome, VR's effect on perceived pain intensity, was assessed by collecting pain scores from participants every 30 seconds while their hands were immersed. We measured pain scores on a 0-10 scale, where 0 represented no pain and 10 represented the most excruciating pain imaginable.¹

Our final secondary outcome, the effects of VR on modulating sympathetic response in the presence of painful stimuli, was assessed by analyzing SCRD (in microsiemens) per 30 second interval. We refer to each of these 30 second intervals as a separate epoch. Skin conductance is expected to increase with increasing sympathetic nervous system activity, as sympathetic activity increases sweat secretion to increase skin conductance.

Sample Size

We considered a hazard ratio of 0.6 to be clinically significant given that it would indicate an approximate 30% improvement in pain tolerance. Assuming an alpha of 0.05 and power of 80%, sample sizes of 30 people in the VR group and 59 people in the control group were needed to be adequately powered to an estimated hazard ratio of 0.6.

Randomization

We randomized participants to their first ice immersion intervention (VR or no VR) and hand use (dominant or non-dominant) using an electronic random number generator with a 1:1 allocation.² Participants then crossed over for their second ice immersion

Statistical Methods

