To analyze the effectiveness of VR on pain tolerance, we analyzed the survival time using a Cox mixed-effect model with trials nested in subject and fit using the coxme package using R software. We controlled for dominant hand treatment assignment, dominant hand order, and gender.

To analyze our secondary outcomes, we used linear mixed effects models with outcomes nested in subject using the lme4 package in R. We controlled for dominant hand treatment assignment, dominant hand order, and gender when analyzing pain perception. The variables in the physiologic model were SCRD change over time and the SCRD change between groups, defined as those with and without VR.

References

- [2] Suresh K. An overview of randomization techniques: An unbiased assessment of outcome in clinical research. *J Hum Reprod Sci*. 2011;4(1):8-11.

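### The pain-score model names no time term although scores exist only during immersion, so a VR effect on tolerance can leak into the pain estimate

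*SAP*

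**What the plan says.** Pain intensity is the first secondary outcome. In SAP Measures it "was assessed by collecting pain scores from participants every 30 seconds while their hands were immersed", and "We measured pain scores on a 0-10 scale". Protocol section 2a, Part 1b, has participants "keep hand submerged as long as they can withstand the cold or until 4 minutes" have passed, so one immersion gives at most 8 scores, and fewer when the hand comes out early.

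SAP Statistical Methods gives the model class: "To analyze our secondary outcomes, we used linear mixed effects models with outcomes nested in subject using the lme4 package in R". For pain it then says "We controlled for dominant hand treatment assignment, dominant hand order, and gender when analyzing pain perception". The next sentence turns to skin conductance: "The variables in the physiologic model were SCRD change over time and the SCRD change between groups". Time is therefore named for one secondary outcome and not for the other. The 30-second unit is defined in the skin conductance paragraph of Measures ("We refer to each of these 30 second intervals as a separate epoch").

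SAP Sample Size sets the planning target for tolerance: "We considered a hazard ratio of 0.6 to be clinically significant given that it would indicate an approximate 30% improvement in pain tolerance". Neither document describes how pain runs over the immersion, gives a typical tolerance time, or says how scores that are absent after withdrawal are treated.

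**The concern.** The number and timing of pain scores depend on tolerance, which is the primary outcome. If VR lengthens immersion, both conditions supply early scores, but the VR immersion of the same person supplies more late ones. A model with VR and the three listed covariates compares the two sets of scores without regard to when they were taken.

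Randomisation and the crossover do not prevent this, because the imbalance arises after the immersion starts. A subject random intercept does not prevent it either. That intercept removes differences between people, and this imbalance lies within a person.

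Three conditions must hold together: no time term was fitted, VR changes immersion time, and pain is not flat over time. If they do, a true pain reduction is understated when pain rises, and VR can appear to reduce pain when it does not if pain falls. The SAP does not let a reader tell whether this was avoided.

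**Working it through.** The SAP gives no figure for the pain model, so there is none to reproduce. From the documents come the 30-second scoring, the 4-minute cap (8 epochs), the crossover, the named covariates and the target hazard ratio (HR) of 0.6. Everything else below is assumed: control median tolerance of 60 s or 120 s, the pain slopes and the standard deviations (SDs).

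**Step 1: imbalance in timing.** With exponential withdrawal and control median m, the proportion still immersed is S(t) = 0.5^(t/m) under control and S(t)^HR under VR. Scores fall at t = 30k, k = 1 to 8. Mean scored epoch = Σ k·S(30k) / Σ S(30k). The late share (120 s or later) is the sum of S(30k) over k = 4 to 8, divided by Σ S(30k).

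| Condition | Mean epoch, m = 60 s | Mean epoch, m = 120 s | Late share, 60 s / 120 s |
|---|---|---|---|
| Control | 6.520/2.263 = 2.881 | 14.344/3.964 = 3.619 | 31% / 46% |
| VR, HR 0.6 | 12.120/3.507 = 3.456 | 20.412/5.154 = 3.960 | 43% / 53% |
| VR, HR 1/1.3 | 9.226/2.885 = 3.198 | 17.537/4.599 = 3.813 | 38% / 50% |

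**Step 2: rough size.** Shift in the VR coefficient ≈ slope per epoch × difference in mean epoch.

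- HR 0.6, differences 0.575 and 0.341: slope 0.25 gives 0.14 / 0.09 points; slope 0.5 gives 0.29 / 0.17.
- HR 1/1.3, differences 0.317 and 0.194: slope 0.5 gives 0.16 / 0.10, a little over half.

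**Step 3: simulation with no true VR effect on pain.** A simulates 60 crossover participants with scores rounded and bounded to 0-10, fitting the listed terms plus VR by REML. B simulates 89 participants with a random-intercept fit that leaves out the hand and gender terms. Both let tolerance vary between people. Entries are the mean VR coefficient without a time term, at control medians 60 s / 120 s.

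| Setting | A | B |
|---|---|---|
| HR 0.6, flat | 0.00 / 0.00 | 0.00 / +0.01 |
| HR 0.6, rising 0.25 | +0.12 / +0.08 | +0.13 / +0.09 |
| HR 0.6, rising 0.5 | +0.23 / +0.17 | +0.23 / +0.17 |
| HR 0.6, falling 0.25 | -0.12 / -0.08 | -0.11 / -0.08 |
| HR 0.6, falling 0.5 | not run | -0.22 / -0.17 |
| HR 1/1.3, rising 0.5 | +0.13 / +0.09 | not run |
| HR 1.0, rising 0.5 | 0.00 / 0.00 | +0.01 / 0.00 |

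A further 60-participant run at HR 0.6, rising 0.5, gave +0.26 / +0.17. A profile that peaks and then declines partly cancels: in B, -0.06 at both medians with a peak at epoch 3, and +0.10 / +0.06 with a peak at epoch 5. With categorical epoch added, the mean coefficient was within 0.02 of zero in every HR 0.6 setting of A and B.

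With a true effect of -1.0 and pain rising 0.5, A gave -0.76 / -0.82 without epoch.

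**Step 4: withdrawal driven by pain.** Here the hand comes out when pain reaches a personal limit that VR raises by 1 point. For slopes 0.25, 0.5 and 1.0 the coefficient was +0.05, +0.17 and +0.38 without epoch, and +0.01, +0.02 and +0.04 with it. It was 0.00 with epoch when only epochs scored under both conditions were kept.

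**Step 5: validity of the test.** Steps 3 and 4 remove the shift in the estimate but do not settle the error rate. The two immersions differ in hand and period, so a person's level may differ between them. With an assumed immersion-level SD of 0.5 (60 s median), epoch plus a subject-only intercept left almost no bias but rejected a true null in 21% of trials at the 5% level. Adding an intercept for immersion within subject brought this to 8%.

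**The case against.** The strongest reply is that the case rests on silence in one sentence. That sentence lists adjustment terms and is not a model formula. It omits VR too, and VR must have been in the model. A reader might infer that the analysis certainly ignored time; the text does not show that, and this part of the reply stands. But VR is implied by the stated outcome, while nothing in the pain text implies epoch. An analyst working from the written terms would leave it out.

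Second, calling the estimate biased presumes a target. The SAP says neither pain at equal immersion time nor average pain over the immersion actually undergone. This stands, so the shift is stated here only relative to the equal-time contrast.

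Third, HR 0.6 is a planning target and not a known effect. The SAP equates it with about a 30% improvement, whereas under exponential withdrawal it means 1/0.6 = 1.67 times the time; 30% longer is HR 1/1.3. This stands and roughly halves the shift.

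Fourth, size and direction come from assumed profiles. A reader might infer that the omission flatters VR. The documents give no pain profile and do not support a direction; with rising pain the error runs against VR. With a true effect of -1.0 the estimate kept its sign in every setting simulated.

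Fifth, a reader might infer that adding epoch to a subject-only intercept gives a valid test at no cost in precision. That holds only without immersion-level variation, and step 5 shows how far it can fail.

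**Conclusion.** The concern holds as a conditional one about a secondary outcome. On the terms the SAP names, the pain model lets a VR effect on tolerance move the pain estimate. The written plan neither rules this out nor shows that it happened.

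Under assumed slopes of 0.25 to 0.5 points per 30 s, the shift is about 0.1 to 0.25 points on 0-10 at HR 0.6 and about half that at HR 1/1.3. It is zero if pain is flat or VR does not change immersion time. The shift is modest in points, but it is a systematic error that a single extra term largely removes. The control medians, slopes, SDs and withdrawal mechanism are assumptions. The primary Cox analysis is unaffected. It should be fixed; confidence is medium, because the fitted model is not documented.

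**What to change.** - State that the target is the VR effect on pain at equal immersion time.
- Write the model in full: score ~ VR + categorical 30-s epoch + dominant-hand treatment + dominant-hand order + gender, with random intercepts for subject and for immersion within subject. The primary Cox model already nests trials within subject.
- Add a sensitivity analysis limited to epochs that the same participant completed under both conditions, because epoch adjustment does not fully remove pain-driven withdrawal.
- The SAP is written in the past tense. If the analysis is done, state whether epoch was fitted, and re-run the pain model if it was not.

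The cost is at most 7 degrees of freedom (8 epochs less 1) on scores already collected, and possibly a re-run of one secondary model. The model assumes one average VR effect across epochs; a VR-by-epoch interaction is optional. The immersion-level intercept makes the standard error somewhat larger. The 8% rejection rate in step 5 is still above 5%, so no claim of an exact error rate should be attached. The sensitivity analysis keeps fewer late scores: in simulation it retained 50-64% of all scores when withdrawal was unrelated to pain (HR 0.6) and 91-96% when pain drove it.
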